6.4.3 MISSED DOSES

Subjects must receive all planned doses in the DLT assessment period in order to be assessed for DLT in Phase 1. Planned doses that are missed can be made up if they are received within the same calendar day of scheduled administration. If a subject misses more than 2 consecutive cycles after completing the DLT assessment period for reasons other than toxicity, the subject will be discontinued unless it is determined that the subject was benefiting from therapy and that the medical monitor permits the subject to resume therapy. See [Section 6.4.1.6](#) for information on cycle delays.

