	
specified by the preexisting dose-escalation plan. Dose escalation will continue in 30 mg increments until the MTD for continuous dosing for Oprozomib ER Tablets is established, as determined by the CSRC and sponsor.
 
• If the MTD for continuous dosing has been established with Oprozomib Tablets, Oprozomib ER tablets will be introduced at the MTD in a cohort of 6 subjects. Escalation beyond this dose can only occur using step-up dosing as described below if there are < 2 DLTs in the 6 subjects in this cohort enrolled with Oprozomib ER Tablets as determined by the CSRC and sponsor. 
Once the MTD for continuous dosing for Oprozomib ER Tablets has been established, step-up dosing will be introduced into dose escalation. Subsequent 2/7 cohorts will be dosed at the 240 mg for 1 cycle then step-up to the dose level to be studied. The rationale for this initial dose is based on safety and tolerability of this dose level in the current study, as no DLTs were observed in this cohort of 3 evaluable subjects at this dose level. The 240 mg dose is 2 dose levels below the single agent MTD, which was found to be 300 mg in Study 2011-001. Subjects on active treatment will continue with Oprozomib ER Tablets under protocol Amendment 4. No changes in drug product, dosage, or treatment regimen occurred in this protocol amendment from the previous version.
 
Determination of the MTD for step-up dosing will be evaluated in the following manner:
 
• The first step-up dosing cohort will start with 1 cycle of 240 mg, and then starting with Cycle 2, subjects will step-up to the MTD from continuous dosing for subsequent cycles.• All subsequent cohorts will also begin dosing at 240 mg for 1 cycle and then will be escalated in Cycle 2 to the step-up dose level to be studied, by 30 mg increments until the MTD is defined with Oprozomib ER Tablets, unless an alternate R2PD is determined by the CSRC and the sponsor. The DLT period will begin in Cycle 2 (the first cycle of dosing at the step-up dose level). 
Phase 2: The Phase 2 portion of the study will include approximately 40 subjects at the recommended dose for each schedule, to better characterize the safety and tolerability, activity, and PK/PDn of the regimen and treatment schedule. The Phase 2 portion of the study for 1 or both treatment schedules will be initiated at the sponsor's discretion.
 
Dose-Limiting Toxicities: During the Phase 1b portion, assessment of DLTs will occur at the following times:
 
• The first 14 days of treatment with continuous dosing (Cycle 1), or• The first 14 days of treatment with the step-up dose to be studied (Cycle 2) 
Any subject who develops DLT after receiving at least 1 dose of oprozomib during the DLT assessment period will be considered evaluable. Any subject who does not develop a DLT but has not received all planned doses of oprozomib and dexamethasone during the DLT assessment period will be considered unevaluable and will be replaced.
 
“Study drug-related” is defined as a reasonable likelihood of clinical causality based on time of event, biology, and dechallenge improvement, and that the adverse event (AE) was not likely explained by the subject's clinical state, underlying disease, concomitant medication, or study/non-study procedure. For the purposes of this study, a DLT is defined as any of the following treatment-related events occurring in the first 14 days of treatment, with treatment at the dose to be studied (i.e., Cycle 1 for continuous dosing or Cycle 2 for step-up dosing):

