3.1.1 PHASE 1B PORTION

Subjects will be evaluated for DLTs according to the National Cancer Institute-Common Terminology Criteria for Adverse Events (NCI-CTCAE), Version 4.03. Subjects with stable disease (SD) or better may continue treatment. Intrasubject dose escalation to the recommended Phase 2 dose may be permitted once that dose has been determined and after

discussion between the treating physician and the **Sponsor** study medical monitor.

The purpose of the Phase 1b portion of the study is to determine the MTD, RP2D, safety, and PK/PDn of oprozomib administered orally once daily in combination with dexamethasone, in subjects with relapsed and/or refractory multiple myeloma, using a 3 + 3 dose-escalation scheme with and without step-up dosing. The maximum tolerated dose is defined as the highest dose level at which fewer than 33% of subjects have a DLT.

For each of the 2 schedules being studied, groups of 3 to 6 subjects will be enrolled into dose-escalation cohorts. As long as fewer than 33% of subjects experience a DLT in a given cohort, escalation will continue by 30 mg increments of oprozomib onto the next designated cohort(s). A minimum of 6 subjects must be treated at the MTD to establish the dose as the MTD with and without step-up dosing.

Assessment of DLTs will occur during the first 14 days of treatment with continuous dosing (Cycle 1) or during the first 14 days of treatment at the step-up dose to be studied (Cycle 2), considered the assessment period. Any subject who develops a DLT during the assessment period after receiving at least 1 dose of oprozomib in the assessment period will be considered evaluable. Any subject who does not develop a DLT during the assessment period, but has not received all planned doses of oprozomib and dexamethasone, will be considered unevaluable and will be replaced.

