6.2.2 DOSE-ESCALATION RULES

The planned and contingent dose levels are provided in Section 3.1.2 (Table 3, Table 4, and Table 5), and dose escalation rules are provided in Table 6. Additional details can be found in the Cohort Management Plan.

Table 6: Dose-Escalation Rules

No. of Evaluable Subjects with Treatment-related DLT at a Given Dose Level	Dose Escalation Rules
0 of 3	Next cohort of 3 subjects treated at the next planned higher dose level.
1 of 3	Up to 3 more subjects are treated at that same dose level.
≥ 2 of 3	Dose escalation stops. Three more subjects will be added to the next lower dose level, unless 6 subjects have already been treated at that dose level.
1 of 6	Next cohort of 3 subjects treated at the next planned higher dose level.
≥ 2 of 6	Dose escalation stops. Additional subjects may be treated at the next lower dose level, for a minimum of 6 subjects treated at that dose level.
Highest dose with < 2 of 6	Maximum tolerated dose

Source: Modified from Simon 1997.

DLT = Dose-limiting toxicity.

Intrasubject dose escalation to the recommended Phase 2 dose may be permitted once that dose has been determined and after discussion between the treating physician and the **Sponsor** medical monitor.

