6.3 DOSE-LIMITING TOXICITY

Subjects will be evaluated for DLT according to the NCI-CTCAE (Version 4.03). Subjects with SD or better may continue treatment.

During the Phase 1b portion, assessment of DLTs will occur during the first 14 days of treatment with continuous dosing (Cycle 1) or during the first 14 days of treatment with the step-up dose to be studied during the 2-week assessment period (Cycle 2). Any subject who develops a DLT during the assessment period after receiving at least 1 dose of oprozomib in the

assessment period will be considered evaluable. Any subject who does not develop a DLT, but has not received all planned doses of oprozomib and dexamethasone, will be considered unevaluable and will be replaced.

Guidelines for withholding study treatment, including treatment delays, reintroduction, and discontinuation, are described in [Section 6.4.1](#). “Study drug-related” is defined as a reasonable likelihood of clinical causality based on time of event, biology, and dechallenge improvement, and that the AE was not likely explained by the subject’s clinical state, underlying disease, concomitant medication, or study/nonstudy procedure. For the purposes of this study, a DLT is defined as any of the following treatment-related events occurring in the first 14 days of treatment, with treatment at the dose to be studied (i.e., Cycle 1 for continuous dosing or Cycle 2 for step-up dosing):

Any \geq Grade 3 nonhematologic AE, with the following exceptions or qualifications:

- \geq Grade 4 abnormalities in serum creatinine or electrolytes will be considered a DLT.
- \geq Grade 3 acute kidney injury, defined as serum creatinine $> 3 \times$ baseline or > 4.0 mg/dL of any duration will be considered a DLT.
- Grade 3 nausea, vomiting, diarrhea, or constipation will be considered a DLT only if lasting for > 7 days despite optimal supportive care, including (at a minimum) a 5-HT₃ antagonist and aprepitant or fosaprepitant for nausea and vomiting, and loperamide (e.g., Imodium), and diphenoxylate/atropine (e.g., Lomotil) for diarrhea.
- Grade 3 fatigue lasting > 14 days will be considered a DLT.
- Asymptomatic Grade 3 hypophosphatemia lasting less than 24 hours will not be considered a DLT.
- \geq Grade 3 dexamethasone-related toxicities will not be considered DLTs.

Any of the following hematologic AEs will be considered a DLT:

- Grade 4 neutropenia: ANC < 500 cells/mcL lasting ≥ 7 days

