8. STUDY TREATMENT DISCONTINUATION

Subjects may discontinue from the study at any time. Subjects who discontinue from study treatment will be monitored for AEs for 30 days after the last dose of oprozomib. In the Phase 1b portion of the study, additional subjects may be enrolled to replace discontinued subjects to reach the target population of MTD-evaluable subjects for each cohort.

For the purposes of estimation of response rate, subjects who discontinue from study treatment before completing a full 14-day cycle (Cycle 1) at the dose or step-up dose to be studied (Cycle 2), do not receive all scheduled doses without a DLT, do not have evaluable disease at Screening, or do not complete a response assessment will be considered unevaluable.

The Sponsor may elect to discontinue the study or either schedule at any time.

The investigator may remove a subject from study treatment for the following reasons:

- Subject with disease progression
- Subject with unacceptable toxicity
- Noncompliance with study procedures
- Need of treatment with medications not allowed by the study protocol
- Subject no longer consents to participate in the study
- Intercurrent illness that interferes with study assessments
- Female subject who becomes pregnant, in which case treatment must be immediately discontinued

The Sponsor or designee must be notified within 24 hours if a subject is discontinued from study treatment.

If the reason for discontinuation is the occurrence of an AE, the subject will be followed by the investigator until such event(s) resolve and/or stabilize, and according to the investigator's judgment, there is no need for further follow-up. The reason for discontinuation from study treatment will be documented on the eCRF.

Additional subjects may be enrolled to account for subjects who have not had adequate safety or efficacy evaluations.

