2 STUDY OVERVIEW

2.1 Overall Study Design

This study is an open-label, Phase 1b/2, multicenter study in which subjects will receive oprozomib (OPZ) administered orally once daily in combination with dexamethasone (DEX) on 2 different treatment schedules. Subjects will receive OPZ on Days 1–5 of a 14-day cycle in combination with 20 mg DEX on Days 1, 2, 8, and 9; or OPZ on Days 1, 2, 8, and 9 of a 14-day cycle in combination with 20 mg dexamethasone on Days 1, 2, 8, and 9. Both the Phase 1b and Phase 2 portions of this trial will be open to subjects with relapsed and/or refractory multiple myeloma.

Treatment will be administered in 14-day cycles until disease progression, unacceptable toxicity, or study treatment discontinuation for any reason.

Disease response assessments will be performed every 4 weeks for the first year through Cycle 26 and then every 8 weeks thereafter according to the IMWG-URC. In addition, nCR and MR will be assessed per the modified EBMT criteria.

A minimum of 3 subjects will be entered within each dose cohort, to be expanded up to 6 subjects if DLTs are observed. Assessment of DLTs will occur during the first 14 days of treatment (or Cycle 1) or the first 14 days of treatment with the step-up dose to be

studies (Cycle 2). Any subject who develops a DLT after receiving at least 1 dose of OPZ will be considered evaluable. Any subject who does not develop a DLT, but has not received all planned doses of OPZ and DEX will be considered unevaluable for the dose escalation decision and will be replaced.

If none of the first 3 subjects in a cohort experiences a DLT in the first cycle, enrollment will commence at the next planned dose level. If 1 of 3 subjects enrolled in a cohort experiences a DLT during the first treatment cycle, the same cohort will be expanded up to 6 evaluable subjects. If 1 of 6 subjects experiences a DLT during the first treatment cycle, the next cohort will enroll at the next higher dose level. If 2 or more subjects in a cohort experience a DLT in the first treatment cycle, the MTD will have been exceeded, additional enrollment within the cohort will cease, and dose escalation will stop.

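### Section 6.4.3 requires all planned doses of every subject before DLT assessment, with no exception for a DLT, and contradicts four statements of who counts (low priority)

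*Protocol*

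**What the plan says.** Protocol Section 6.4.3 (Missed Doses) opens: "Subjects must receive all planned doses in the DLT assessment period in order to be assessed for DLT in Phase 1". It then allows a missed dose to be made up only on the same calendar day. It does not refer to Section 6.3.

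Four other places define who counts for DLT:

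- Synopsis, Dose-Limiting Toxicities: "Any subject who develops DLT after receiving at least 1 dose of oprozomib during the DLT assessment period will be considered evaluable".
- Protocol Section 3.1.1: evaluable status goes to "Any subject who develops a DLT during the assessment period after receiving at least 1 dose of oprozomib" in that period.
- Protocol Section 6.3 has the same rule. It confines the full-dosing condition to one group, who are unevaluable and replaced: "Any subject who does not develop a DLT, but has not received all planned doses of oprozomib and dexamethasone".
- SAP Section 2.1: "Any subject who develops a DLT after receiving at least 1 dose of OPZ" is evaluable, and again only DLT-free subjects need all planned doses.

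Two sentences in Protocol Section 8 are related. In Phase 1b, "additional subjects may be enrolled to replace discontinued subjects to reach the target population of MTD-evaluable subjects for each cohort"; this sentence does not mention DLTs. On the separate question of response rate, Section 8 treats as unevaluable those who "do not receive all scheduled doses without a DLT", so there the missed-dose clause does carry the DLT qualifier.

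The escalation rules in Table 6 (Section 6.2.2) act on the "No. of Evaluable Subjects with Treatment-related DLT at a Given Dose Level".

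**The concern.** The subjects most likely to miss a planned dose because of toxicity are those with a DLT. Table 8 generally prescribes a hold for Grade 3 and discontinuation for Grade 4 nonhematologic toxicity. Table 7 prescribes a hold for ANC below 500 or platelets below 25,000 cells/mcL. Section 6.4.1.6 permits no dosing delays in the assessment period. A subject whose DLT on Day 2 leads to the remaining doses being held is therefore a counted DLT under Section 6.3, but could not be assessed under the literal words of Section 6.4.3.

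An omission of this kind is not neutral. Removing a DLT from the Table 6 count can move the decision towards escalation or leave it unchanged. It can never move it towards stopping.

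**Working it through.** **1. The texts compared.** The documents give no figure for this point, so the first step is a comparison of wording.

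| Subject | Synopsis, 3.1.1, 6.3, SAP 2.1 | 6.4.3 read literally |
|---|---|---|
| DLT, all planned doses received | counted | counted |
| DLT after at least 1 oprozomib dose, later dose missed | counted as a DLT | not assessed |
| No DLT, all planned doses received | counted | counted |
| No DLT, a dose missed | unevaluable, replaced | not assessed |

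The two rules differ only in the second row. Section 6.4.3 does not mention replacement. A subject *discontinued* for a DLT could be replaced through Section 8 if Section 6.4.3 were taken to decide who is MTD-evaluable. For a DLT subject whose dose is only *held*, no text states a replacement.

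**2. Where Table 6 is sensitive.** Replace one DLT subject by a DLT-free one, so that x of n becomes (x − 1) of n. Table 6 gives these actions: 0 of 3, escalate; 1 of 3, add up to 3; 2 or more of 3, stop; 1 of 6, escalate; 2 or more of 6, stop. I treat 0 of 6 as fewer than 2 of 6.

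| True count | Action | Count after swap | Action | Changed? |
|---|---|---|---|---|
| 1 of 3 | add up to 3 | 0 of 3 | escalate | yes |
| 2 of 3 | stop | 1 of 3 | add up to 3 | yes |
| 3 of 3 | stop | 2 of 3 | stop | no |
| 1 of 6 | escalate | 0 of 6 | escalate | no |
| 2 of 6 (33%) | stop | 1 of 6 (17%) | escalate | yes |
| 3, 4, 5 or 6 of 6 | stop | 2, 3, 4 or 5 of 6 | stop | no |

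Of the 3 + 6 = 9 counts with at least one DLT, 3 change the action, all towards escalation. If the omitted subject is not replaced, these three counts become 0 of 2, 1 of 2 and 1 of 5, for which Table 6 has no row.

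**3. Illustration under assumed inputs.** Let p be the true DLT rate and f the share of DLT subjects who miss a later planned dose. The documents give neither. If every such subject were dropped and replaced, the counted DLT rate would be q = p(1 − f)/(1 − pf). The 3+3 probability of escalating is (1 − q)³ + 3q(1 − q)⁵. For example, p = 0.33 and f = 0.5 give q = 0.165/0.835 = 0.198, and 0.517 + 0.197 = 0.714.

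| p | f = 0 (Section 6.3 rule) | f = 0.25 | f = 0.5 | f = 0.75 |
|---|---|---|---|---|
| 0.33 | 0.43 | 0.56 | 0.71 | 0.89 |
| 0.50 | 0.17 | 0.27 | 0.43 | 0.71 |

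This shows sensitivity and does not estimate bias. It also assumes replacement of held subjects, which no text states.

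**4. The reported data.** Sections 1.4.3 and 1.5.1 report 3 DLTs at 210 mg on the 5/14 schedule, with 7 subjects treated there. The evaluable number is not given, so 7 is an upper limit. Leaving out one DLT gives 2 of at most 6, and escalation still stops. In fact all three were reported as DLTs, and the 180 mg cohort was then expanded.

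**The case against.** The best defence is context. Section 6.4.3 concerns missed doses and sits under dose adjustments. Its opening sentence can be read as a compliance instruction that shortens the rule for DLT-free subjects. Section 6.3 is the dedicated DLT section, and three other places agree with it. Section 6.4.3 never uses the words evaluable or replaced, so the link to Section 8 is an inference. The DLT listing in Section 10.3.3 has no dose-completion condition. This makes the intent clear, but the sentence still does not say what is intended.

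The exposed group is also narrower than it first appears, and this stands. On 5/14 the last oprozomib dose is on Day 5, and only dexamethasone remains, on Days 8 and 9. Tables 7 and 8 direct oprozomib. Under Section 6.4.2 dexamethasone stops along with oprozomib only on permanent discontinuation. A 5/14 DLT arising after Day 5 that leads only to an oprozomib hold therefore misses no planned dose. The 2/7 schedule, with oprozomib on Days 8 and 9, is more exposed.

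The 3-of-9 count is not a probability, and this also stands. It pools two designs. A 3+3 cohort expanded from 1 of 3 can reach at most 4 of 6, so its tally is 3 of 7. For cohorts enrolled directly as six it is 1 of 6.

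Finally, the Cohort Safety Review Committee reviews all clinical and laboratory data before escalation (Section 6.2.1), and further detail lies in a Cohort Management Plan that is not among the documents. Amendment 4 follows completion of the primary analysis and only pares down data collection (Section 1, Appendix N). These points limit the practical importance. They do not remove the contradiction.

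**Conclusion.** The concern holds. The first sentence of Section 6.4.3 is current protocol text and conflicts with the synopsis, Sections 3.1.1 and 6.3, and SAP Section 2.1. If followed literally, it errs in the unsafe direction, and it would change the Table 6 action at 1 of 3, 2 of 3 and 2 of 6 when the omitted subject is replaced by a DLT-free one. The size of any bias cannot be stated without the share of DLT subjects who miss a later planned dose.

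The practical risk is low: the correct rule appears four times, the committee sees all the data, the main analysis is complete, and the reported DLTs were counted. This is a wording correction of low priority. It does not suggest that the trial's dose decisions were wrong.

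**What to change.** Replace the first sentence of Section 6.4.3 with:

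> Subjects who do not have a DLT must receive all planned doses of oprozomib and dexamethasone in the DLT assessment period to be evaluable; a subject with a DLT after at least 1 dose of oprozomib in that period is counted regardless of later missed doses.

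This restates Section 6.3. Section 8 then needs no change, because MTD-evaluable has a single meaning, and SAP Section 2.1 is already correct.

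The cost is one sentence, with no added subjects, procedures or analyses. Sections 12.2 and 13.1 require IRB/IEC approval before an amendment is implemented, and about 16 sites are planned (12 in the US and 4 in France). It is therefore sensible to make the change with the next amendment, or to record it as a clarification, and not to amend for this alone. The faulty sentence should not be carried into later protocols.

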6.5 SAFETY GUIDANCE FOR INVESTIGATORS

Based on the experience in nonclinical studies of oprozomib and available Phase 1 clinical data in subjects with solid tumors and hematologic malignancies, the following guidance is recommended but not mandated to investigators unless otherwise noted in the dose reduction guidelines:

- Subjects with active systemic infections of any kind should not be dosed with oprozomib until infection has resolved. Subjects with neutrophil counts related to their infection of $ANC < 500$ cells/mcL should not be treated until the neutrophil count has recovered to > 1500 cells/mcL.
- For platelet counts $< 25,000$ cells/mcL, oprozomib dosing should be held until platelet count is $\geq 25,000$ cells/mcL independent of platelet transfusions for 1 week. Consideration of dose reduction of oprozomib should be given if it is thought that oprozomib may have caused the thrombocytopenia.

- Subjects should have anemia corrected in accordance with the institutional guidelines, which can include transfusions or support with erythropoietin or darbepoetin.
- Based on the high incidence of nausea and vomiting that has been observed to date, it is recommended that subjects treated with oprozomib receive prophylactic antiemetics that would typically be utilized to prevent nausea and vomiting prior to moderately to highly emetogenic therapies.
- Prophylactic treatment for diarrhea is not recommended; however, subjects who experience diarrhea should be treated with antidiarrheals and may be given prophylaxis once they are known to have diarrhea related to administration of oprozomib.
- Hypophosphatemia has been observed in a few subjects treated with oprozomib. Severe hypophosphatemia has also been observed in subjects treated with other proteasome inhibitors, including carfilzomib (data on file), bortezomib (Messinger 2010), and MLN 9708 (Richardson 2012). This typically has been transient and not associated with clinical symptoms. Subjects should be monitored carefully for electrolyte abnormalities, and electrolytes should be replaced as needed.
- Cases of TLS have been observed with proteasome inhibitors, including oprozomib. It is recommended that all subjects begin vigorous oral hydration (1.5–2.0 liters/day) the day before and on days of oprozomib dosing until instructed that the risk of TLS has abated. Allopurinol prophylaxis and close monitoring of fluid and electrolyte balance are recommended for subjects with renal functional impairment and for those with a high tumor burden. For specific recommendations, see Section 6.6.1.
- Gastrointestinal hemorrhage has been reported in subjects treated with oprozomib, including fatalities. Subjects with Grades 3 and 4 GI hemorrhage should not be rechallenged with oprozomib and should be permanently discontinued. Endoscopy should be considered for any subject developing GI hemorrhage.

See Section 6.4.1 for additional information and recommendations for dose adjustments required for specific hematologic and nonhematologic toxicities.

